10.9. Appendix 8: Abbreviations and Definitions

CONFIDENTIAL

enter	Participants entered into a study are those who sign the informed consent form directly or through their legally acceptable representatives.
GCP	good clinical practice
GIP	glucose-dependent insulinotropic peptide
GIPR	GIP receptor
GLP-1	glucagon-like peptide 1
IB	Investigator's Brochure
ICF	informed consent form
ICH	International Council for Harmonisation
IEC	Independent Ethics Committees
IP	investigational product
IRB	Institutional Review Boards
ISR	injection-site reaction
informed consent	A process by which a participant voluntarily confirms their willingness to participate in a particular study, after having been informed of all aspects of the study that are relevant to the participant's decision to participate. Informed consent is documented by means of a written, signed and dated informed consent form.
investigational product	A pharmaceutical form of an active ingredient or placebo being tested or used as a reference in a clinical trial, including products already on the market when used or assembled (formulated or packaged) in a way different from the authorized form, or marketed products used for an unauthorized indication, or marketed products used to gain further information about the authorized form. See also "IMP."
medication error	Errors in the prescribing, dispensing, or administration of a study intervention, regardless of whether or not the medication is administered to the participant or the error leads to an AE. Medication error generally involve a failure to uphold one or more of the five "rights" of medication use: the right participant, the right drug, the right dose, right route, at the right time.
	In addition to the core five rights, the following may also represent medication errors:
	• dose omission associated with an AE or a product complaint
	dispensing or use of expired medication
	• use of medication past the recommended in-use date
	• dispensing or use of an improperly stored medication
	• use of an adulterated dosage form or administration technique inconsistent with the medication's labeling (for example, Summary of Product Characteristics, IB, local label, protocol), or
	• shared use of cartridges, prefilled pens, or both.

CONFIDENTIAL

misuse	Use of a study intervention for self-treatment that either is inconsistent with the prescribed dosing regimen, indication, or both, or is obtained without a prescription

2. ABBREVIATIONS

Abbreviations pertain to the Statistical Analysis Plan (SAP) only (not the tables, figures and listings [TFLs]).

%AUC(t_{last} - ∞) Percentage of AUC(0- ∞) extrapolated

AE Adverse event

Ae_(t1-t2) Amount of dose excreted in breastmilk within the time interval t1 to

t2

AUC Area under the concentration versus time curve

 $AUC(0-\infty)$ Area under the concentration versus time curve from time zero to

infinity

AUC(0-t_{last}) Area under the concentration versus time curve from time zero to

time t, where t is the last time point with a measurable concentration

BQL Below the quantifiable lower limit of the assay

CL/F Apparent total body clearance of drug calculated after extra-vascular

administration

C_{last} Last quantifiable drug concentration

C_{max} Maximum observed drug concentration

CRF Case Report Form

CRU Clinical Research Unit
CSR Clinical Study Report
CV Coefficient of variation

DMP Data Management Plan

ECG Electrocardiogram

Fe_(t1-t2) Fraction of dose excreted in breastmilk within the time interval t1 to

t2

ICF Informed consent form

ICH International Conference on Harmonisation

LLOQ Lower limit of quantification

M/P Milk to plasma ratio

MedDRA Medical Dictionary for Regulatory Activities

MRE Magnetic resonance elastography

PG Plasma Glucose
PK Pharmacokinetic

CONFIDENTIAL

CONFIDENTIAL

3. INTRODUCTION

This SAP has been developed after review of the Clinical Study Protocol (final version dated 17 May 2023).

This SAP describes the planned analysis of the safety, tolerability and pharmacokinetic (PK) data from this study. A detailed description of the planned TFLs to be presented in the clinical study report (CSR) is provided in the accompanying TFL shell document.

The intent of this document is to provide guidance for the statistical and PK analyses of data. In general, the analyses are based on information from the protocol, unless they have been modified by agreement with Eli Lilly and Company. A limited amount of information concerning this study (e.g., objectives, study design) is given to help the reader's interpretation. This SAP must be finalized prior to first participant visit. When the SAP and TFL shells are agreed upon and finalized, they will serve as the template for this study's CSR.

This SAP supersedes the statistical considerations identified in the protocol; where considerations are substantially different, they will be so identified. If additional analyses are required to supplement the planned analyses described in this SAP, they may be performed and will be identified in the CSR. Any substantial deviations from this SAP will be agreed upon with Eli Lilly and Company and identified in the CSR. Any minor deviations from the TFLs may not be documented in the CSR.

This SAP is written with consideration of the recommendations outlined in the International Conference on Harmonisation (ICH) E9 Guideline entitled Guidance for Industry: Statistical Principles for Clinical Trials¹ and the ICH E3 Guideline entitled Guidance for Industry: Structure and Content of Clinical Study Reports².

4. STUDY OBJECTIVES AND ENDPOINTS

Objectives	Endpoints
Primary	
To evaluate tirzepatide PK in	Area under the tirzepatide concentration-time curve
breastmilk of healthy lactating females	in breastmilk from time zero extrapolated to infinity
	$[AUC(_{0-\infty}]$
Secondary	
CCI	

CONFIDENTIAL

5. STUDY DESIGN

This is a postmarketing, single-site, open-label, single-treatment arm, single-dose, lactation study, assessing PK of tirzepatide in breastmilk and plasma in healthy lactating women.

Approximately 14 healthy lactating females will be enrolled so that about 8 females complete the study.

Participants will receive a single dose of tirzepatide CCI delivered by subcutaneous injection.

The study duration for individual participants, inclusive of screening, is expected to be approximately 8 weeks.

Screening

Screening may occur up to 27 days prior to Day -1. During the screening visit, participants will undergo screening tests as mentioned in the protocol. Participants who are not enrolled within 28 days of screening may be subject to an additional medical assessment, clinical measurements, or both, to confirm their eligibility. In such instances, at a minimum, the following screening tests and procedures should be repeated:

- weight
- vital signs
- safety 12-lead electrocardiogram (ECG)
- clinical laboratory tests, and
- pregnancy test.

Inpatient Treatment Period

Participants will be admitted to the clinical research unit (CRU) on Day -1 to establish baseline measurements.

Participants will receive a single subcutaneous (SC) tirzepatide dose on Day 1 following overnight fasting of approximately 8 hours. Participants will remain in the CRU until Day 5 following the completion of study procedures. The inpatient stay for the participant may be extended at the clinical discretion of the investigator (for example, necessary for the participant's clinical wellbeing and management and monitoring of adverse events (AEs)).

Breastmilk and plasma samples for tirzepatide PK will be collected. Breastmilk volume will be measured across the study duration as indicated in the protocol. Safety will be assessed by physical examination, medical assessments or both, vital signs, ECGs, safety laboratory tests, glucose safety monitoring, and the recording of AEs. Breastfeeding must be discontinued prior to the administration of tirzepatide and for the duration of the study.

CONFIDENTIAL

Outpatient Follow-up Period

On Days 6, 8, 15 ± 1 , and 22 ± 1 , participants may either return to the CRU for outpatient visits or have these visits be performed remotely by home health nurses as deemed appropriate by the study investigator. On Day 29 ± 1 , the participants will return to the CRU for the final follow-up visit.

6. BLINDING

This is a non-randomized, open-label study.

7. TREATMENT

The study treatment name "CC tirzepatide SC" will be used in the TFLs.

A footnote stating "Abbreviations: SC = subcutaneous" will be utilized.

8. SAMPLE SIZE JUSTIFICATION

Approximately participants will be enrolled so that about participants provide evaluable PK data. Since inter-participant variability of primary PK parameter in breastmilk is unknown, sample size is not chosen to achieve a specific precision in estimation of the primary endpoint.

9. DEFINITION OF ANALYSIS POPULATIONS

The "Enrolled" population will consist of all participants who signed the informed consent form (ICF), regardless of whether they take any doses of Tirzepatide.

The "Safety" population will consist of all participants who received a single SC dose of tirzepatide, whether or not they completed all protocol requirements. Participants will be analyzed according to the intervention they actually received.

The "Pharmacokinetic" population will consist of all participants who received a single SC dose of tirzepatide and have evaluable PK samples.

All protocol deviations that occur during the study will be considered for their severity/impact and will be taken into consideration when participants are assigned to analysis populations.

10. STATISTICAL METHODOLOGY

10.1 General

Data listings will be provided for all data that is databased. Summary statistics and statistical analysis will only be presented for data where detailed in this SAP. For continuous data, summary statistics will include the arithmetic mean, arithmetic standard deviation (SD), median, minimum, maximum, and number of observations; for log-normal data (e.g., the PK parameters: area under the concentration versus time curves (AUCs) and C_{max}) the geometric mean and geometric coefficient of variation (CV%) will also be presented. For categorical data, frequency count and percentages will be presented. Data listings will be provided for all participants up to the point of withdrawal, with any participants excluded from the relevant population highlighted.

CONFIDENTIAL

Summary statistics and statistical analyses will generally only be performed for participants included in the relevant analysis population. For the calculation of summary statistics and statistical analysis, unrounded data will be used.

For change from baseline summary statistics, each individual change from baseline will be calculated by subtracting the individual participant's baseline value from the value at that time point. The individual participants' change from baseline values will be used to calculate the summary statistics (arithmetic mean, arithmetic SD, median, minimum, maximum, and number of observations) using a SAS procedure such as Proc Univariate.

Data analysis will be performed using SAS® Version 9.4 or greater.

10.2 Demographics and Participant Disposition

Participant disposition will be listed. The demographic variables age, sex, race, ethnicity, country of enrolment, site ID, body weight, height, and body mass index (BMI) will be summarized and listed. All other demographic variables will be listed only.

10.3 Pharmacokinetic Assessment

10.3.1 Pharmacokinetic Analysis

The following PK parameters will be determined where possible from the plasma and breast milk concentrations of tirzepatide (LY3298176) using noncompartmental methods in validated software program Phoenix WinNonlin (Certara, Version 8.1 or higher):

Parameter	Units ^a	Definition
AUC _(0-tlast)	h.ng/mL	area under the concentration-time curve from time 0 to the time of the last observable concentration $(t_{\text{last}})^b$
$\mathrm{AUC}_{(0-\infty)}$	h.ng/mL	area under the concentration-time curve from time 0 to infinity ^b
$\%AUC_{(tlast-\infty)}$	%	fraction of $AUC_{(0-\infty)}$ extrapolated
C_{max}	ng/mL	maximum observed concentration
t_{max}	h	time of the maximum observed concentration
t_{last}	h	time of the last quantifiable concentration
t _{1/2}	h	half-life associated with the terminal rate constant (λz) in non-compartmental analysis
CL/F	L/h	apparent total clearance (plasma only)
V_z/F	L	apparent volume of distribution during the terminal phase (plasma only)
M/P		Milk to plasma ratio, calculated as $AUC_{0-\infty, \text{ breastmilk}} / AUC_{0-\infty, \text{ plasma}}$
$Ae_{(t1-t2)}$	mg	amount of dose excreted in breastmilk within the time interval t1 to t2
$Fe_{(t1-t2)}$	%	fraction of dose excreted in breastmilk within the time interval t1 to t2

^a Units are based on concentration units (provided by the bioanalytical lab or preferred units for presentation of PK parameters) and dose units used in the study.

CONFIDENTIAL

b The AUC will be calculated using a combination of the linear and logarithmic trapezoidal methods (linear-log trapezoidal rule)

Additional PK parameters may be calculated, as appropriate. The software and version used for the final analyses will be specified in the CSR. Any exceptions or special handling of data will be clearly documented within the final CSR.

Formatting of tables, figures and abbreviations will follow the Eli Lilly Global PK/PD/TS Tool: NON-COMPARTMENTAL PHARMACOKINETIC STYLE GUIDE. The version of the tool effective at the time of PK analysis will be followed.

General PK Parameter Rules

- Actual sampling times will be used in the final analyses of individual PK parameters, except for pre-dose sampling times which will be set to zero.
- The actual start times of each breastmilk collection will be used for the calculation of individual breastmilk PK parameters.
- C_{max} and t_{max} will be reported from observed values. If C_{max} occurs at more than one time point, t_{max} will be assigned to the first occurrence of C_{max} .
- AUC parameters will be calculated using a combination of the linear and logarithmic trapezoidal methods (linear-log trapezoidal rule). The linear trapezoidal method will be applied up to t_{max} and then the logarithmic trapezoidal method will be used after t_{max}. The minimum requirement for the calculation of AUC will be the inclusion of at least three consecutive concentrations above the lower limit of quantification (LLOQ), with at least one of these concentrations following C_{max}. AUC_(0-∞) values where the percentage of the total area extrapolated is more than 20% will be flagged. Any AUC_(0-∞) value excluded from summary statistics will be noted in the footnote of the summary table.
- Half-life (t_{1/2}) will be calculated, when appropriate, based on the apparent terminal log-linear portion of the concentration-time curve. The start of the terminal elimination phase for each participant will be defined by visual inspection and generally will be the first point at which there is no systematic deviation from the log-linear decline in plasma concentrations. Half-life will only be calculated when a reliable estimate for this parameter can be obtained comprising of at least 3 data points. If t_{1/2} is estimated over a time window of less than 2 half-lives, the values will be flagged in the data listings. Any t_{1/2} value excluded from summary statistics will be documented in the footnote of the summary table.
- A uniform weighting scheme will be used in the regression analysis of the terminal log-linear portion of the concentration-time curve.
- The parameters based on predicted last quantifiable drug concentration (C_{last}) will be reported (except in bioequivalence and bioavailability studies, where only the observed parameters will be reported).

CONFIDENTIAL

Individual PK Parameter Rules

- Only quantifiable concentrations will be used to calculate PK parameters with the
 exception of special handling of certain concentrations reported below the lower limit of
 quantitation (BQL). Concentrations reported as BQL will be set to a value of zero when
 all of the following conditions are met:
 - o The compound is non-endogenous.
 - The samples are from the initial dose period for a participant or from a subsequent dose period following a suitable wash-out period.
 - o The time points occur before the first quantifiable concentration.
- All other BQL concentrations that do not meet the above criteria will be set to missing.
- Also, where two or more consecutive concentrations are BQL towards the end of a
 profile, the profile will be deemed to have terminated and therefore any further
 quantifiable concentrations will be set to missing for the calculation of the PK parameters
 unless it is considered to be a true characteristic of the profile of the drug.

Individual Concentration vs. Time Profiles

- Individual concentrations will be plotted utilizing actual sampling times.
- The terminal point selections will be indicated on a semi-logarithmic plot.

Average Concentration vs. Time Profiles

- The average concentration profiles will be graphed using scheduled (nominal) sampling times
- The average concentration profiles will be graphed using arithmetic average concentrations.
- The pre-dose average concentration will be set to zero. Otherwise, only quantifiable concentrations will be used to calculate average concentrations.
- Concentrations at a sampling time exceeding the sampling time window specified in the protocol, or \pm 10%, will be excluded from the average concentration profiles.
- Concentrations excluded from the mean calculation will be documented in the final CSR.
- A concentration average will be plotted for a given sampling time only if 2/3 of the individual data at the time point have quantifiable measurements that are within ± 10% of the nominal time. An average concentration estimated with less than 2/3 but more than 3 data points may be displayed on the mean concentration plot if determined to be appropriate and will be documented within the final CSR.

CONFIDENTIAL

Treatment of Outliers during PK Analysis

Application of this procedure to all PK analyses is not a requirement. Rather, this procedure provides justification for exclusion of data when scientifically appropriate. This procedure describes the methodology for identifying an individual value as an outlier for potential exclusion but does not require that the value be excluded from analysis. The following methodology will not be used to exclude complete profiles from analysis.

Data within an Individual Profile

A value within an individual profile may be excluded from analysis if any of the following criteria are met:

- For PK profiles during single dosing of non-endogenous compounds, the concentration in a pre-dose sample is quantifiable.
- For any questionable datum that does not satisfy the above criteria, the profile will be evaluated and results reported with and without the suspected datum.

Data between Individual Profiles

- 1. If n<6, then the dataset is too small to conduct a reliable range test. Data will be analyzed with and without the atypical value, and both sets of results will be reported.
- 2. If n≥6, then an objective outlier test will be used to compare the atypical value to other values included in that calculation:
 - a. Transform all values in the calculation to the logarithmic domain.
 - b. Find the most extreme value from the arithmetic mean of the log transformed values and exclude that value from the dataset.
 - c. Calculate the lower and upper bounds of the range defined by the arithmetic mean ±3*SD of the remaining log-transformed values.
 - d. If the extreme value is within the range of arithmetic mean $\pm 3*SD$, then it is not an outlier and will be retained in the dataset.
 - e. If the extreme value is outside the range of arithmetic mean $\pm 3*SD$, then it is an outlier and will be excluded from analysis.

If the remaining dataset contains another atypical datum suspected to be an outlier and $n \ge 6$ following the exclusion, then repeat step 2 above. This evaluation may be repeated as many times as necessary, excluding only one suspected outlier in each iteration, until all data remaining in the dataset fall within the range of arithmetic mean $\pm 3*SD$ of the log-transformed values.

CONFIDENTIAL

Reporting of Excluded Values

Individual values excluded as outliers will be documented in the final CSR. Approval of the final CSR will connote approval of the exclusion.

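### Applied to every clean sample of 8, the SAP's between-profile outlier rule drops a genuine value about 25% of the time and cuts 95% CI coverage to about 88–90%; its use is left to judgement and no all-data result is required at n≥6

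*SAP*

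**What the plan says.** SAP 10.3.1, under the heading on data between individual profiles, splits by sample size.

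- Below n=6 no test is made: "Data will be analyzed with and without the atypical value, and both sets of results will be reported".
- At n≥6 all values are log-transformed and the one furthest from the mean is set aside. It is then compared with mean ± 3 SD of the values that remain. If it lies outside, "then it is an outlier and will be excluded from analysis".
- The step may be repeated while at least six values are left, "excluding only one suspected outlier in each iteration, until all data remaining in the dataset fall within the range of arithmetic mean" ± 3 SD.

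The opening paragraph of the outlier procedure reads differently. "Application of this procedure to all PK analyses is not a requirement", and the procedure "does not require that the value be excluded from analysis". It adds: "The following methodology will not be used to exclude complete profiles from analysis".

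On reporting, "Individual values excluded as outliers will be documented in the final CSR", and the AUC rules state that any AUC(0-∞) "value excluded from summary statistics will be noted in the footnote of the summary table". For n≥6 the SAP does not ask for a summary that keeps the excluded value.

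SAP 10.3.2 makes breastmilk AUC(0-∞) the primary parameter, reported as a geometric mean with a 95% confidence interval. SAP 5 expects about 14 enrolled and about 8 completing.

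**The concern.** A 3 SD limit sounds strict. Here the SD comes from only n−1 values, with the most extreme one deliberately left out, so at small n the limit is easily crossed by genuine data. The interval is then calculated as if nothing had been selected out. It comes out too narrow.

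Whether a value leaves the primary summary is also not fixed in advance. The opening paragraph makes exclusion optional, while the last step of the test makes it automatic. The sentence protecting complete profiles is unclear for this endpoint: each participant contributes one breastmilk profile and one AUC(0-∞), and the SAP does not say whether removing that AUC counts as removing a profile. In an open-label study the decision is made by people who have seen the values.

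The geometric mean and its interval are the main quantitative output of a study meant to inform advice on tirzepatide in milk. Losing a genuine high value understates milk exposure.

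**Working it through.** **Inputs.** From SAP 10.3.1: log scale, limit of mean ± 3 SD of the remaining n−1 values, repeats only while at least 6 values remain. From SAP 10.3.2: 95% interval for the geometric mean. From SAP 5: about 8 completers and 14 enrolled. The number of evaluable AUC(0-∞) values is not known, so n=6 to 14 was examined. Assumed: log-normal AUC with no true outliers, and a Student t interval on the log scale. Drop rate and coverage do not depend on the CV. The plan gives no error rate for the rule, so there is no figure to reproduce.

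**How strict the limit is.** Expressed in SDs of the full sample, the limit is

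z = [3(n−1)/n] / √{[(n−2) + 9(n−1)/n]/(n−1)}.

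- n=8: 2.625/√(13.875/7) = 1.86
- n=14: 2.786/√(20.357/13) = 2.23

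**Chance of dropping a genuine value.** Lying more than 3 leave-one-out SDs from the leave-one-out mean is the same as |t| > 3/√(1+1/(n−1)) on n−2 degrees of freedom. Summing over the n values bounds the chance that at least one is dropped:

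- n=6: cut-off 2.739, 6 × 0.0520 = 0.312
- n=8: cut-off 2.806, 8 × 0.0309 = 0.247
- n=14: cut-off 2.891, 14 × 0.01355 = 0.190

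**Simulation of the rule applied to every sample** (1,000,000 clean samples per variant at n=8, 300,000 at each other n):

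| n | Samples losing at least one value | Coverage, one pass | Coverage, repeated |
|---|---|---|---|
| 6 | 31% | 87.7% | 87.5% |
| 7 | 27% | 88.9% | 86.7% |
| 8 | 25% | 89.8% | 87.9% |
| 10 | 21–22% | 91.1% | 89.8% |
| 12 | 20% | 91.9% | 90.8% |
| 14 | 19% | 92.3% | 91.5% |

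With all values kept, coverage is 95.0%. At n=6 no repeat is possible, so the two entries there differ only by simulation error.

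The loss at n=8 comes entirely from samples with an exclusion. Their coverage is 74% after one pass and 66% with repeats, and their median interval width is 0.71 or 0.66 of the all-data width. One pass: 0.248 × 0.741 + 0.752 × 0.950 = 0.898.

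**Discretionary use** (n=8, one pass, separate run of 400,000 samples). If the rule is invoked in a random share of the samples that would trigger it, coverage is 95.0% at no use, 93.8% at a quarter, 92.5% at half, 91.2% at three quarters and 89.9% at full use. With repeats, half use gives 91.4%.

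**If only high values were judged atypical** (n=8): 12.4% of samples are affected. The interval lies wholly below the true value in 5.1% of samples and wholly above in 2.5%, so coverage is 100 − 5.1 − 2.5 = 92.4%.

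**Size of the shift when a high value is dropped.** The documents give no CV for milk AUC. Assumed CVs of 30%, 50% and 100% give log SDs, √ln(1+CV²), of 0.29, 0.47 and 0.83. Among samples in which the top value is removed, the reductions are:

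| Assumed CV | Geometric mean (median), n=8 | Upper limit, n=8 | Geometric mean (median), n=14 | Upper limit, n=14 |
|---|---|---|---|---|
| 30% | 8% | 14% | 5% | 9% |
| 50% | 12% | 22% | 8% | 13% |
| 100% | 20% | 35% | 14% | 22% |

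**The case against.** The strongest reply is that the SAP does not apply the rule to every sample. Someone must first call a value atypical, and exclusion is described as optional, so 25% and 88–90% are always-apply figures rather than expected performance. That is right, and the range for partial use is given for that reason. But the final step still directs exclusion, and a judgement made after seeing the data is no safeguard when the test so often confirms a genuine extreme.

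Second, the sentence on complete profiles may protect a participant's only AUC(0-∞), in which case this rule could not touch the primary summary. That reading is possible. The SAP does not state it, and its AUC rules do foresee excluded AUC(0-∞) values, although next to the flag for more than 20% extrapolation.

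Third, exclusions are visible: they are footnoted, documented in the clinical study report, and the data are listed (SAP 10.1). A reader could recompute the all-data result, but the reported interval would still be the selected one. The SOP cited in Protocol Appendix 7 and the table shells are not public and could require more, so the gap is established only for the public text.

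Fourth, the rule helps when a value really is aberrant. With one of 8 values shifted by 5 log SDs, it cuts bias in the log mean from 0.62 to 0.03 SD, with 94.7% coverage; keeping everything gives a very wide interval with 98.8%. At a 3 SD shift the rule's coverage is 92.7%. This benefit is a reason to keep the outlier-excluded result as a sensitivity analysis.

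Finally, the test is two-sided, so the high-only case is a scenario and not something the plan states. The analysis is also descriptive, and no precision target was set. If fewer than 6 values are evaluable, both results are already required.

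**Conclusion.** The concern holds. For clean log-normal data and 8 evaluable values, routine use of the rule drops a genuine value in about 25% of samples and gives 88–90% coverage for a nominal 95% interval. At 14 values the figures are about 19% and 91.5–92.3%. Under the discretion the SAP allows, coverage at n=8 lies somewhere from about 88% to 95%, depending on how often and how many times the rule is invoked, and so cannot be stated beforehand. Footnotes and report entries disclose an exclusion but do not repair the interval.

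The drop rates and coverage rest on log-normality, a log-scale t-interval and the assumed n. The sizes of the shifts also rest on assumed CVs and apply only when a high value is removed. The conflict over whether exclusion is optional, the unclear sentence on complete profiles, and the lack of a required all-data result at n≥6 need none of these assumptions. This should be fixed.

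**What to change.** In SAP 10.3.1:

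1. Reconcile the opening paragraph with the last step of the n≥6 test: state whether exclusion is optional or required, and whether the sentence on complete profiles covers a participant's AUC(0-∞).
2. Base the primary geometric mean and 95% interval on every participant in the pharmacokinetic population with an evaluable breastmilk AUC(0-∞). Permit removal from the primary result only for a documented assay, sampling or dosing error.
3. Where the outlier test flags a value, report the outlier-excluded geometric mean and interval as a labelled sensitivity analysis at any n. This extends what the SAP already does below n=6.

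Under the assumptions above, keeping all values restores 95.0% coverage. The cost is SAP wording, one extra table row and a primary interval that may be wider.
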